9.1 Appendix 1: Regulatory, Ethical, and Study Oversight Considerations

9.1.1 Regulatory and Ethical Considerations

This study will be conducted in accordance with the protocol and with the Consensus ethical principles derived from international guidelines including the Declaration of Helsinki and Council for International Organizations of Medical Sciences (CIOMS) International Ethical Guidelines, ICH Good Clinical Practice (GCP) Guidelines and applicable laws and regulation.

The protocol, protocol amendments, informed consent form and Investigator Brochure must be reviewed and approved to the institutional review board and independent ethics committee before the study is initiated. Any amendments to the protocol will require approval before implementation of changes made to the study design, except for changes necessary to eliminate an immediate hazard to study participants.

The investigator will be responsible for providing written summaries of the status of the study to the relevant authorities in accordance with their requirements and notify them of any significant safety findings. The investigator is also responsible for providing oversight of the conduct of the study at the site and adherence to relevant regulations.

9.1.2 Informed Consent Process

The investigator or his/her representative will explain the nature of the study to the participant and answer all questions regarding the study. Participants must be informed that their participation is voluntary. Participants will be required to sign a statement of informed consent that meets the requirements of local regulations. Participants must be re-consented to the most current version of the informed consent form during their participation in the study and a copy must be provided to the participant.

9.1.3 Data Protection

Participants will be assigned a unique identifier by the sponsor. The participant must be informed that his/her personal study-related data will be used by the sponsor in accordance with local data protection law. The level of disclosure must also be explained to the participant who will be required to give

consent for their data to be used as described in the informed consent. The participant must be informed that his/her medical records may be examined by auditors or other authorized personnel appointed by the sponsor, institutional review board, independent ethics committee or regulatory authorities.

9.1.4 Dissemination of Clinical Study Data

Study design and results will be registered at the US National Institutes of Health's website www.clinicaltrials.gov. Trial results will be disseminated through non-promotional, peer-reviewed publications. Access to analyzable datasets from the clinical study can be granted through a secure system, following an independent assessment of the scientific merit of a rigorously defined research question from a third party.

9.1.5 Data Quality Assurance

All participant data relating to the study will be recorded on electronic case report file (eCRF). The investigator is responsible for verifying that data entries are accurate and correct by physically or electronically signing the CRF. Guidance on completion of CRFs will be provided in investigator brochure and eCRF. The investigator must permit study-related monitoring and regulatory reviews, audits and inspections. The investigator must provide direct access to source data documents. Monitoring details are provided in the monitoring plan and contracts. The sponsor or designee is responsible for the data management of this study including quality checking of the data and the sponsor assumes accountability for actions delegated to other individuals. Records and documents, including signed informed consent forms, pertaining to the conduct of this study must be retained by the investigator for 15 years after study completion. No records may be destroyed or transferred to another location or party during the retention period without the written approval of the sponsor.

9.1.6 Source Documents

Source documents provide evidence for the existence of the participant and substantiate the integrity of the data collected. Source documents are filed at the investigator's site. Data entered in the eCRF that are transcribed from source documents must be consistent with the source documents or the discrepancies must be explained. Definition of what constitutes source data can be found in the investigator brochure. Study monitors will perform ongoing source data verification to confirm that data entered into the eCRF by authorized site personnel are accurate, complete, and verifiable from source

documents; that the safety and rights of participants are being protected; and that the study is being conducted in accordance with the currently approved protocol and all applicable regulatory requirements.

9.1.7 Study and Site Start and Closure

Study start

The study start date is the date on which the clinical study will be open for recruitment of participants.

Study Termination

The sponsor or designee reserves the right to terminate the study at any time for any reason at the sole discretion of the sponsor. Reasons for the early closure of a study by the sponsor or investigator may include but are not limited to: Failure of the investigator to comply with the protocol, the requirements of the institutional review board, independent ethics committee or local health authorities, the sponsor's procedures, or GCP guidelines, inadequate or no recruitment or total number of participants included earlier than expected.

If the study is prematurely terminated or suspended, the sponsor shall promptly inform the investigators, independent ethics committee and institutional review board and the regulatory authorities of the reason for termination or suspension, as specified by the applicable regulatory requirements. The investigator shall promptly inform the participant and should assure appropriate participant therapy and/or follow-up.

9.1.8 Publication Policy

Authorship will be determined by mutual agreement and in line with International Committee of Medical Journal Editors authorship requirements.

9.2 Appendix 2: Clinical Laboratory Tests

The tests detailed in Table 6 will be performed at the hospital laboratory for any hospital visit including the standardized preplanned 6. month visits for the “Usual care” arm, unscheduled visits, early discontinuation visits and at study end visit. Patients will be instructed to take blood tests each 3rd month. The patient’s general practitioner will be responsible for these blood tests in the two, new follow-up strategy arms. If there are safety issues or adverse events, the general practitioner will contact HPs at the hospital. Patients, who normally take the 3-month blood tests at the hospital due to convenience, may continue this practice. Every 6th month the patients in the two intervention arms will take a photo of the laboratory test results and upload this in the MyDignio app. For the “Remote monitoring” study arm, the laboratory test results will be monitored each 6th month, whereas for the “Patient-initiated care”, the laboratory test results will only be used for research purposes after the 18-month follow-up. Additional tests may be performed at any time during the study as determined necessary by the medical doctor or required by local regulations. Medical doctors must document their review of each laboratory safety report.

Table 6: Protocol-Required Safety Laboratory Tests

Laboratory Tests	Parameters
Hematology	Hemoglobin Red blood cells White blood cell count with Differential: Neutrophils, Lymphocytes, Monocytes, Eosinophils, Basophils Platelet Count
Clinical Chemistry	Creatinine Glomerular filtration rate Alanine transaminase

9.3 Appendix 3: AEs and SAEs: Definitions and Procedures for Recording, Evaluating, Follow-up, and Reporting

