5.1.4 Patient-initiated care arm

Patients in this arm will also download the app, MyDignio, on their smartphone or tablet and receive a brief introduction from the study coordinator. The app will be used to collect PROs. Patients are instructed to contact the hospital if they need an evaluation regarding medication, symptoms worsening or adverse events. The patients will receive a SMS reminder for “tasks” (e.g. self-reporting or uploading a photo with blood test results each 6 months) according to the planned time points as outlined in 7.2-7.3. The patients will receive an automatic reminder if the task is not completed.

Table 1: Indication for unscheduled/extra visits for all three study arms

Indication	Definition	Action
Significant worsening	Patient-reported significant symptoms worsening	The HP excludes other potential reasons for the experienced worsening. If there is a need for changing medication, a physical examination or blood test, a visit will be scheduled within two weeks
Significant adverse effects	Safety laboratory test results showing adverse effects or patient-reported adverse events	Schedule a visit within two weeks

Table 2: Indication for the HPs to contact a patient in the Remote monitoring study arm

Indication	Definition	Action
Significant worsening	Yellow flag: BASDAI ≥ 4 in the monthly PRO reporting Red flag: BASDAI ≥ 8 in the monthly PRO reporting	The study nurse contacts the patient to evaluate if a hospital visit is needed
The patient has requested to be contacted by HP	The patient sends a message in MyDignio app asking to be contacted by HP	The study nurse contacts the patient to evaluate if a hospital visit is needed

¹ PGA: Patient Global Assessment of disease activity

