7.2.3 Laboratory assessment

Assessment of inflammatory markers will be performed prior to each hospital visit by the hospital laboratory and includes ESR (mm/hr) and CRP (mg/L). All patients will be instructed to take standard care blood samples (hemoglobin, red blood cells, white blood cells with differential count, platelets, creatinine, and alanine transaminase) as a safety procedure when using TNFi as prescribed and monitored by their general practitioner. Patients, who normally take these blood tests at the hospital due to convenience, may continue this practice. Patients in the “Remote monitoring” and the “Patient-initiated care” arms are instructed to report blood test results each 6th month in the MyDignio app. These blood tests will in addition be used to assess clinical safety (see 7.3.3). A small subgroup in the Remote monitoring group will receive a CRP-instrument and be asked to measure their CRP monthly and register the value in the MyDignio app.

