7.3.1 Physical Examinations

- General clinical examination (baseline visit)

7.3.2 **Vital signs**

- Pulse and blood pressure (baseline visit)
- Height and weight (baseline visit)

7.3.3 **Clinical Safety Laboratory Assessments** (every 3rd month and all visits)

- Haemoglobin, red blood cells, white blood cells with differential count and platelet count
- Glomerular filtration rate (GFR) and creatinin
- Alanine transaminase (ALT)

7.3.4 **Adverse Events (AEs), Serious Adverse Events (SAEs), and Other Safety Reporting**

The definitions of adverse events (AEs) and serious adverse events (SAEs) as well as the method of recording, evaluating, and assessing causality of AEs and SAEs and the procedures for completing and transmitting SAE reports are provided in Appendix 3.

7.3.5 **Time Period and Frequency for Collecting AE and SAE Information**

All AEs and SAEs will be collected from the start of intervention until the final follow-up visit at the time points specified in Schedule of Activities. Medical occurrences that begin before the start of study intervention, but after obtaining informed consent, will be recorded as Medical History/Current Medical Conditions, not as AEs. All SAEs, including updates, will be recorded and reported to the sponsor or designee immediately, as indicated in Appendix 3. Investigators are not obligated to actively seek information on AEs or SAEs after conclusion of the study participation.

7.3.6 **Method of Detecting AEs and SAEs**

Care will be taken not to introduce bias when detecting AEs and/or SAEs. Open-ended and non-leading verbal questioning of the participant is the preferred method to inquire about AE occurrences.

7.3.7 **Follow-up of AEs and SAEs**

After the initial AE/SAE report, the investigator is required to proactively follow each participant at subsequent visits/contacts. All SAEs will be followed until resolution, stabilization, the event is otherwise explained, or the participant is lost to follow-up.

7.3.8 **Regulatory Reporting Requirements for SAEs**

Prompt notification by the investigator to the sponsor of an SAE is essential so that legal obligations and ethical responsibilities are met. The sponsor has a legal responsibility to notify both the local regulatory authority and other regulatory agencies about the safety of a study intervention under clinical

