8.4.4 Safety Analysis

Rates and type of adverse events and serious adverse events in all three study arms will be reported.

9 Supporting Documentation and Operational Considerations

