9.3.1 Definition of AE

AE Definition

An AE is any untoward medical occurrence in a clinical study participant, temporally associated with the use of study intervention, whether or not considered related to the study intervention.

NOTE: An AE can therefore be any unfavorable and unintended sign (including an abnormal laboratory finding), symptom, or disease (new or exacerbated) temporally associated with the use of study intervention.

Events Meeting the AE Definition

- Any abnormal laboratory test results or other safety assessments, including those that worsen from baseline, considered clinically significant in the medical and scientific judgment of the investigator.
- Exacerbation of a chronic or intermittent pre-existing condition including either an increase in frequency and/or intensity of the condition.
- New conditions detected or diagnosed after study intervention even though it may have been present before the start of the study.
- Signs, symptoms, or the clinical sequelae of a suspected overdose of either TNFi or a concomitant medication. Intentional overdose taken with possible suicidal/self-harming intent should be reported regardless of sequelae.
- The signs, symptoms, and/or clinical sequelae resulting from lack of efficacy will be reported as AE or SAE if they fulfil the definition of an AE or SAE.

Events NOT Meeting the AE Definition

- Any clinically significant abnormal laboratory findings or other abnormal safety assessments which are associated with the underlying disease, unless judged by the investigator to be more severe than expected for the participant's condition.
- The disease/disorder being studied or expected progression, signs, or symptoms of the disease/disorder being studied, unless more severe than expected for the participant's condition.
- Medical or surgical procedure: the condition that leads to the procedure is the AE.
- Situations in which an untoward medical occurrence did not occur (social and/or convenience admission to a hospital).
- Anticipated day-to-day fluctuations of pre-existing disease(s) or condition(s) present or detected at the start of the study that do not worsen.

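### Site review of month-6 and month-12 safety blood results is put off until adverse-event collection has closed in patient-initiated care only, so laboratory adverse events can be under-ascertained in that arm

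*Protocol*

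**What the plan says.** **What counts.** Section 9.3.1 includes abnormal laboratory results among adverse events when they are "considered clinically significant in the medical and scientific judgment of the investigator".

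**Who sees the results.** Appendix 2 (9.2) has the hospital laboratory run the safety tests at hospital visits, including the usual-care visits and the study-end visit. In both new arms the general practitioner is responsible for the 3-monthly tests, and patients upload a photo of the results every sixth month. The remote-monitoring uploads are monitored at that interval. For patient-initiated care, "the laboratory test results will only be used for research purposes after the 18-month follow-up".

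**When events are collected.** Section 7.3.5: "All AEs and SAEs will be collected from the start of intervention until the final follow-up visit at the time points specified in Schedule of" (the quote stops one word short of the schedule's full title). Investigators then have no obligation to seek events actively once participation has ended.

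**How they are compared.** Comparing safety between strategies is a secondary objective (2.3.4). Section 8.4.4: "Rates and type of adverse events and serious adverse events in all three study arms will be reported".

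**Statements that point the other way.**
- Section 7.2.3, directly after describing the uploads of both new arms: "These blood tests will in addition be used to assess clinical safety (see 7.3.3").
- Table 1, which covers all three arms, lists as a reason for a visit "Safety laboratory test results showing adverse effects or patient-reported adverse events".
- 9.2 itself requires doctors to document their review of every laboratory safety report.

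**The concern.** A laboratory adverse event under 9.3.1 needs an investigator to see the value and judge it. If one arm's values reach the investigator later than the others', the recorded rates in 8.4.4 partly measure who looked and when.

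The events at stake are largely silent: low white cells or platelets, raised ALT, reduced renal function. The Schedule of Activities has an adverse-event review at months 6, 12 and 18, but 7.3.6 prefers open verbal questioning, which is poorly suited to finding abnormalities without symptoms. An abnormality present at month 6 or 12 and gone by month 18 is put before the site in two arms and may not be in the third.

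The bias would run towards fewer recorded events in patient-initiated care. In a trial asking whether follow-up can safely be reduced, that is the unfavourable direction. The point concerns laboratory-defined events only, not symptomatic events or the primary endpoint.

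**Working it through.** The protocol gives no figure on this point to reproduce, so the check sets the sections side by side and then uses a simple model for scale.

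**Step 1: first laboratory reader at each draw** (Schedule of Activities footnote 2, 5.1.1, 7.2.3, 9.2)

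| Draw (month) | Usual care | Remote monitoring | Patient-initiated care |
|---|---|---|---|
| 3, 9, 15 | general practitioner | general practitioner | general practitioner |
| 6, 12 | site | site (upload monitored) and general practitioner | general practitioner; upload held until after month 18 |
| 18 | site | site | site |

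The site sees 3 of 3 half-yearly results inside the collection window in usual care and remote monitoring, and 1 of 3 in patient-initiated care. The general-practitioner route for months 3, 9 and 15 is normally shared by all arms. Patients who usually have blood taken at the hospital may continue to do so. The table ignores them because their number is not given.

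**Step 2: capture model.** These are assumptions, not protocol values:
- abnormalities are spread evenly over the six draws, and each is visible at one draw only;
- the site captures everything it reads;
- general practitioners relay a share g of what they read;
- nothing found in the held uploads is entered later.

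Share captured:
- usual care and remote monitoring: (3 + 3g)/6
- patient-initiated care: (1 + 5g)/6

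Relative deficit = [(3 + 3g) - (1 + 5g)] / (3 + 3g) = 2(1 - g)/(3 + 3g)

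| g | Other arms | Patient-initiated | Relative deficit |
|---|---|---|---|
| 0 | 3/6 = 50% | 1/6 = 17% | 2/3 = 67% |
| 0.5 | 4.5/6 = 75% | 3.5/6 = 58% | 1/4.5 = 22% |
| 0.75 | 5.25/6 = 87.5% | 4.75/6 = 79% | 0.5/5.25 = 9.5% |
| 1 | 100% | 100% | 0% |

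The deficit is below 10% when 2 - 2g < 0.3 + 0.3g, that is g > 1.7/2.3 = 0.74.

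**Step 3: counts.** With 80 patients per arm and an assumed true 18-month risk of 6% (80 x 0.06 = 4.8 events), g = 0.5 gives 4.8 x 0.75 = 3.6 recorded events in each of the other arms and 4.8 x 3.5/6 = 2.8 in patient-initiated care. With an assumed 12% (9.6 events) the figures are 7.2 and 5.6. The difference in recorded counts is then about one to two events, but in a table of such small numbers it matters for the comparison.

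**The case against.** The best defence is that 9.2 restricts only the trial's use of the uploaded photo. The general practitioner reads the tests as they are taken and is told to contact the hospital about safety issues or adverse events. Table 1 then leads to a visit, and 9.2 has the safety tests run at unscheduled visits. Less monitoring is also what defines this arm. Safety variables will be summarised descriptively (8.4.1), and analysis detail is left to an analysis plan that is not at hand.

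Much of this stands, and it rules out four stronger readings that a reader might infer:
- *The results go unread until month 18.* They do not; the general practitioner monitors them. What is deferred is the site's use of the uploads.
- *Every abnormal result is an adverse event.* Section 9.3.1 requires the investigator to judge it clinically significant.
- *Month-6 and month-12 abnormalities can never be recorded.* Section 7.3.5 removes the duty to seek events after participation ends. It does not bar late entry of an event dated inside the window, but it does not provide for it either.
- *Two thirds of that arm's laboratory events are lost.* That needs g = 0, which contradicts the instruction to general practitioners, and it needs every abnormality to be transient.

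What remains is the asymmetry. The general-practitioner route is broadly common to all arms, whereas site reading at months 6 and 12 is an addition that only patient-initiated care lacks. The protocol states no threshold for the general practitioner's contact. Reduced monitoring may be the intended intervention, but unequal counting of outcomes need not follow from it. A descriptive summary of laboratory values does not remove the asymmetry from the adverse-event rates.

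**Conclusion.** The point holds as a risk of differential under-ascertainment, of unknown size. The protocol fixes different site-side review of laboratory results by arm while making the investigator's judgment the condition for a laboratory adverse event. Under the model's assumptions the relative deficit in patient-initiated care runs from 67% (no relay) to none (complete relay), and is below 10% if general practitioners relay more than about 74%. The protocol gives no relay share, so none of these values is an estimate. Abnormalities that persist to month 18, or late entry of events found in the uploads, would make the deficit smaller.

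Independently of any bias, 9.2 does not fit with 7.2.3, with Table 1, or with its own sentence on documented review. The risk table in 2.3.1 adds to this: for both new arms it warns that adverse events may go undetected if patients fail to register blood results, so it treats those results as a means of detection.

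**What to change.** 1. **7.3.5:** state that abnormalities in month-6 and month-12 results count by sampling date, even if the site reads them after month 18.
2. **8.4.4:** add a laboratory-abnormality comparison from the recorded values of the 7.3.3 tests at months 6, 12 and 18, in all three arms. Use one pre-specified rule applied without knowledge of arm. The cut-offs are for the sponsor to set; the limits in 4.2 are only one option, and they would miss worsening from baseline that stays within them. Report this separately from investigator-judged events.
3. **8.4.4:** note that investigator-judged laboratory events were ascertained differently by arm. Item 2 does not correct those rates; it gives a comparison that does not depend on who read the result.
4. **Reconcile** the research-only use in 9.2 with 7.2.3, Table 1 and the documented-review sentence in 9.2. Whether and how these results are used during the study is for the sponsor to settle; no clinical rule is proposed here.

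Items 1 to 3 cost a few lines of text and one extra table. The values are already planned to be uploaded or held in the hospital record, so no new data collection is needed.
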